The labelling, filling of placebo bottles and distribution of the study medication to the study centers will be performed at a certified pharmacy (Graz or Salzburg).

Concomitant interventions

Routine low-dose vitamin D supplementation (≤ 800 IU/day) is allowed during the study period and will be documented.

Adherence assessment

At visit 4 (Day 90), compliance will be assessed using the percentage of actually taken doses compared to the prescribed doses (self reported or reported by the caregivers).

Active vitamin D metabolites

Although in the future it will be interesting and necessary to assess the potential need for additional active vitamin D in critical illness, and specifically acute/chronic kidney failure, we choose not to do so in this trial because of simplicity and costs.

STEERING COMMITTEE

The steering committee consists of the PI and the co-investigators.

VISIT PLAN / STUDY PROCEDURES

SCHEDULE OF EVALUATIONS

ASSESSMENT	Screening VISIT -1	Enrollment Baseline data, loading dose VISIT 1	VISIT 2	VISIT 3	VISIT 4	VISIT 5
	Day -9 to Day 0	Day 0	Day 5	Day 28	Day 90	Month 12
Time window (days)			±2		±14	±30
25(OH)D	X					
inclusion/exclusion criteria	X	X				
signed informed consent if possible, otherwise deferred/surrogate	X	X				
randomisation		X				
demographics		X				
SAPS III		X				
TISS 28		X				
Charlson comorbidity index		X				
Stool sample (microbiome, subgroup) (optional, for Medical University Graz centers only)		X	X			
SAFETY EVALUATION						
Serum calcium	X	X	X	(X)		
Falls					X	
Fractures					X	
New episodes of nephrolithiasis					X	
Intervention						
Loading dose 540,000 IU		X				
Daily dose 4,000 IU			X	X	X	
Outcome variables						
Mortality			X	X	X	X
SOFA		X	X			
qSOFA		X				
Number of organ failures		X	X			
Infections requiring antibiotics					X	
Hospital and ICU readmission					X	

Discharge disposition					X	
Katz Activity of Daily Living		X			X	
25(OH)D (optional, for Medical University Graz centers only)		X	X			
1,25(OH)2D (optional, for Medical University Graz centers only)		X	X			

VISIT -1 (SCREENING)

25(OH)D screening is performed within clinical routine of the trial sites. Screening should be performed within the first 72 hours after ICU admission, and 25(OH)D routine testing should be available within 72 hours. After a patient has been identified to be eligible for the trial, the study medication should be given within 72 hours (max. 9 days).

If the major inclusion criterion of severe vitamin D deficiency is met, the other inclusion and exclusion criteria are evaluated by the local investigator/s at Visit 1. Informed consent will be ascertained whenever possible.

BASELINE ASSESSMENTS

- Age
- Sex
- ICU admission diagnosis
- ICU type
- Charlson comorbidity index
- SAPS III
- TISS 28
- 25(OH)D routine testing
- qSOFA
- Katz Activities of daily life

At baseline, data on demographic and clinical characteristics of the patients are obtained. At Centers of Medical University Graz it is planned to take a blood sample before the loading dose on day 0 and day 5 to ascertain biochemical response. The samples will be stored frozen at -70 C until batch analysis. In this subgroup (Medical University Graz), also stool samples will be collected for microbiome analysis on day 0 and day 5 . Stool samples are stored at -80°C

The Charlson comorbidity index, SAPS III and TISS 28 will be determined to be able to adjust for severity of illness and preexisting comorbidities.

RANDOMIZATION AND BLINDING

Patients will be randomly assigned to either placebo or vitamin D3 in a 1:1 ratio, using the web-based randomization service "Randomizer for Clinical Trials" developed at the Institute for Medical Informatics, Statistics and Documentation, Medical University of Graz. Patients will be stratified according to trial site (ICU) and gender. An independent statistician will set up the study in the Randomizer.

The following method will be used to maintain the blind: the randomization list from the randomizer.at will be kept strictly confidential and no routine vitamin D testing is done after study inclusion. The independent statistician and unblinded pharmacist will keep treatment allocation information confidential until database lock.

In case of safety concerns (eg. severe hypercalcemia > 3.5 mmol/L), participants of the study may be unblinded by the local investigator at each participating site and/or the coordinating center. This will be done and documented with the Randomizer.

VISIT 1

Study medication

The day of the study medication loading dose is day 0. This is also the start for the calculation of the time dependent outcome data.

VISIT 2 (DAY 5 ±2)

At day 5, extensive clinical and laboratory data will be collected, including several measures of severeness of morbidity. It is likely that the majority of all patients will still be hospitalized. In the unlikely case a patient will be discharged before day 5 the data will be collected at discharge (day 3 or day 4).

VISIT 3 (DAY 28)

At visit 3, the primary endpoint (28-day mortality) will be assessed. For Austria, this information may be collected from Statistik Austria. Otherwise, this information will be obtained by the research team including nurses through the patient data management system and/or telephone.

VISIT 4 (Day 90 ± 14d)

A follow up visit will be done by telephone 90 days after study inclusion by each study center: 1) family physician and/or 2) patient and/or 3) hospital). This visit will include important safety evaluations and secondary outcomes. This is also the end of the active intervention.

VISIT 5 (1 year ± 1 month)

A final follow up visit (with results reported separately) will be done by telephone after 1 year. For Austria, Statistik Austria will be contacted first.

COMPLETION

The database lock will take place after the 90-day follow up of the last patient has been completed, all queries have been sufficiently well addressed and implemented in the database (applicable for the interim and the final analysis).

UNBLINDING FOR INTERIM AND FINAL ANALYSIS

For the formal planned interim analysis the DSMB statistician will get the unblinding list from the independent statistician responsible for the randomization procedure.

For the final analysis the unblinding list will be given to the study statisticians after database lock.

SAFETY ASSESSEMENTS

SAFETY MONITORING (SERUM CALCIUM, RENAL FUNCTION, FALLS AND FRACTURES)

Because of extremely high event rate in ICU patients and the well known risk profile of vitamin D3, safety monitoring will be restricted to known vitamin D-related adverse events.

Calcium and creatinine will be monitored regularly for routine purposes during ICU stay and recorded in the eCRF. Patients will be asked for new episodes of nephrolithiasis, falls and fractures at the 90-day-follow up telephone visit.

ADVERSE EVENT REPORTING

Only potential study drug-related adverse events (hypercalcemia, new episodes of nephrolithiasis, falls, and fractures) will be monitored and recorded up to 90 days.

Details will be specified in a separate document (SOP Reporting of SAE in intensive care – version June 2016). No separate reporting of rehospitalization or death will be performed because of the expectedly high event rates in the setting of critical illness.

STOPPING RULES FOR THE TRIAL OVERALL

29/40

VITDALIZE study protocol, 1.3, 24.01.2018

A DSMB will monitor trial progress and safety. Should safety concerns evolve, the DSMB might recommend stopping the study at any time. There will be one planned interim analysis for efficacy. In case of overwhelming benefit the DSMB can recommend stopping the trial.

DATA SAFETY MONITORING BOARD (DSMB)

- [name], Prof. em., Critical Care, University Hospital Geneva
- [name], Prof., Department of Geriatrics, University of Zurich
- [name], Department of Statistics, Medical University of Vienna

STATISTICAL CONSIDERATIONS

The statistical analysis here presented will be detailed in a Statistical Analysis Plan (SAP). Should the SAP and this protocol differ, the methods in the SAP prevail. The SAP will be finalized before database lock for the planned interim analysis.

DEFINITION OF ANALYSIS SETS

Study participants who do not provide an informed consent after regaining consciousness and refuse to provide any more information are excluded from the study and will not be included in any statistical analysis.

INTENTION-TO-TREAT POPULATION

The primary analysis will be performed on the intention-to-treat population (ITT). The ITT will include all patients who receive at least the loading dose of the study medication. All patients included here will be analysed according to the treatment assignment during randomisation.

PER PROTOCOL POPULATION

The per protocol population will include all patients who received the loading dose and have a compliance > 80%. Compliance is defined as self reported percentage of doses ingested until day 90. Other major protocol violations may also lead to exclusion of patients from the per protocol population. This will be discussed on an individual basis within the study team.

SAFETY POPULATION

The safety analyses will be based on the treated set, which is defined as all randomized patients who receive at least one dose of trial medication. All patients will be analysed according to the treatment they actually received.

DATA ANALYSIS

General aspects

All clinical and safety data collected in the study will be analysed with SAS v9.4 procedures in a Windows XP environment. Data will be presented as summary tables and, where appropriate, as plots. Continuous data will be described by means, standard deviations, medians and upper and lower quartiles unless otherwise stated. The number of observations and minimum and maximum values are also included. All descriptive summaries will be displayed to one more decimal place than actually measured. Categorical data will be summarized using frequencies and percentages.

Demographic and Baseline Characteristics

In a summary of demographic, baseline and diagnostic characteristics (age, weight, height, sex, SAPS III, Charlson comorbidity index, qSOFA - criteria, laboratory parameters,...) a comparison of the treatment groups will take place. To this end, appropriate descriptive and inferential statistics will be applied. Relevant medical history will be also displayed using summary statistics according to the two treatment groups.

Analysis of primary outcome

The primary outcome will be 28-day mortality defined as time from application of the study medication loading dose (day 0) to day 28 or death. Kaplan Meier estimates of survival curves in each treatment arm will be displayed. Group comparison will be made using a two-sided log rank test. Additionally, a hazard ratio with a 95% confidence interval will be computed from an univariate Cox-proportional hazards regression. Furthermore sensitivity analyses using multivariable Cox-proportional hazards regression will be performed adjusting for important clinical parameters. Details will be defined in the SAP.

Analysis of secondary outcomes

ICU, hospital mortality, 90-day mortality and 1-year mortality will be analysed as the primary outcome. ICU and hospital length of stay are defined as time between application of the study medication (day 0) and discharge at the primary ICU/hospital; readmissions and stays

at other hospitals will not be added, date and hour will be recorded, in case of a missing hour, the time 12am will be used.

At day 5 the SOFA Score is recorded. Organ failures (> 2 SOFA points in each of the 6 categories) will be reported in total and for each organ system separately. To compare the laboratory parameters 25(OH)D and 1,25(OH)₂D levels ANCOVA will be used.

At day 90, Katz Activities of Daily Life Score, infections requiring antibiotics and hospital and ICU readmission will be assessed. The Self – reported infections requiring antibiotics and hospital and ICU readmission will be categorized as yes/no. Additionally, the number of infection episodes, number of antibiotics and -discharge disposition (home, rehabilitation, other hospital) will be presented. Comparison between groups will be performed using non-parametric tests and Chi-square tests.

Stool samples

In a subgroup, stool samples will be collected for microbiome analysis on day 0 and day 5. Stool samples are stored at -80°C. DNA extraction from stool samples will be performed by mechanical lysis with a MagnaLyser Instrument (Roche Diagnostics, Mannheim, Germany) and subsequent total bacterial genomic DNA isolation with the MagNA Pure LC DNA Isolation Kit III (bacteria, fungi) in a MagNA Pure LC 2.0 Instrument (Roche Diagnostics) according to the manufacturer's instructions. For amplification of bacterial 16S rRNA the template-specific sequence AGAGTTTGATCCTGGCTCAG and CTGCTGCCTYCCGTA, targeting the hypervariable region V1-V2 of the 16S rRNA gene, are used. PCR reactions for each sample are performed in triplicates. Subsequently the amplicons are purified according to standard procedures, quantified, pooled and sequenced with the MiSeq Reagent Kits v3 (600 cycles, Illumina, Eindhoven, Netherlands) according to manufacturer's instructions with 20% PhiX (Illumina). The generated FASTQ files are used for microbiota analysis. Raw reads from Illumina MiSeq are pre-processed and filtered using MOTHUR v.1.31. Reads are de-noised using PyroNoise and chimera-filtered with UCHIME. Pyrosequencing errors are reduced with pre.cluster and non-bacterial sequences were also excluded. High quality reads are aligned to the SILVA database and taxonomy was assigned by MOTHUR's implementation of the ribosomal database project (RDP)-classifier followed by binning into phylotypes based on taxonomy. The shared file is then converted into a biom table and passed on to QIIME's (v.1.9.1) core_diversity.py command using non-phylogenetic parameters.

Analysis of safety outcomes

The safety outcomes, (hypercalcemia on day 5, new kidney stones, self-reported falls, and fractures until day 90) will be analysed as binary variables and compared with Chi-square tests.

Subgroup analysis

Predefined subgroup analyses will be performed for all primary and secondary outcomes based on the following group definitions as exploratory analysis:

- Kidney function (CKD 4 or lower vs. higher at inclusion)
- Sepsis (admission diagnosis) vs. non sepsis defined by the 2016 criteria (suspected infection/qSOFA on day 0 – respiratory rate of 22/min or greater, altered mentation, or systolic blood pressure of 100 mm Hg or less (57))

MISSING DATA HANDLING

All available data will be used in the analyses and data summaries. There will be no imputation of any missing data.

SAMPLE SIZE AND INTERIM ANALYSIS

Sample size considerations

The sample size is based on the primary endpoint 28-day mortality. In the VITdAL-ICU study (2014), 28-day mortality rates of 36% (37/102) in the placebo group and 20% (20/98) in the Vitamin D Group were observed (51). In this multicenter study we assume 28-day mortality rates of 25% in the placebo group versus 20% in the vitamin D group. We assume that baseline (placebo) mortality will be lower in this study because in contrast to the previous VITdAL-ICU study, academic and non-academic smaller sites with patients with a lower severity of illness will participate.

Using a fixed sample size design and a two-sided log-rank test for equality of survival curves with a two-sided alpha level of 5%, a sample size of n=1093 per group will be needed to achieve a power of 80% (total sample size of 2186). The **Table** below shows the sample sizes when the assumptions about 28-day mortality rates are varied between 25% - 35% for the Placebo group and between 20% - 30% for the vitamin D group as well as when the observed 28-day mortality rates from Amrein et al (2014) are assumed.

Placebo 28-day mortality	25%		30%		Based on the VITdAL-ICU study
Alpha level	0.05	0.05	0.05	0.05	0.05
Placebo proportion alive (π_P) at time t	0.75	0.75	0.70	0.70	0.637
VitD proportion alive (π_{VitD}) at time t	0.80	0.81	0.8	0.75	0.796
Hazard ratio $\ln(\pi_{\text{VitD}})/\ln(\pi_P)$	0.78	0.73	0.63	0.81	0.51
Power (%)	80	90	80	80	80
n per group	1093	1002	296	1245	129
Total number of events required	486	434	143	679	68
N Total	2186	2004	592	2490	258

Table: Different sample size scenarios using a two-sided log rank test

One interim analysis will be conducted when 50% of planned enrolled patients in each arm have completed their day 28 assessment (Visit 3) or prematurely discontinued the study. This interim analysis is intended to test for efficacy, i.e. the trial will be terminated after the interim analysis, if the main question can already be answered at this interim analysis.

Using a O'Brien-Fleming spending function (60) a total sample size of at least N=2194 (494 events) is required to achieve 80% power. With this sample size a hazard ratio of 0.78 (for survival rates of 0.8 in the Vitamin D group and 0.75 in the Placebo group corresponding to a 5% absolute 28-day mortality difference) can be detected, using a 2-sided log rank test with 0.05 alpha level assuming that the hazards are proportional. Accounting for a drop-out rate of approximately 10% yields a total sample size of N=2400 patients. A **power of 90%** would be achieved with a similar sample size if the treatment effect is larger (Hazard Ratio 0,73, or a 6% absolute 28-day mortality difference).

Planned interim analysis

One formal interim analysis by the Data Safety Monitoring Board (DSMB) will be performed at inclusion of 50% (N=1200) of patients having their day 28 assessment completed or discontinued the study. The interim analysis will take place approximately 12-18 months after start of the study. If the interim analysis shows a benefit for the vitamin D group, the DSMB may recommend early study termination.

The interim analysis will be performed only for the primary outcome 28 day mortality. The O'Brien-Fleming rule will be used to stop the trial early for efficacy. In detail, if the p-value of the log rank test is smaller than 0.003, then the trial can be stopped early by the DSMB.

Only the primary endpoint will be assessed for the interim analysis with an alpha level of 0.003. It is planned to test the secondary efficacy variables and the safety outcomes at an alpha level of 0.05. We will specify this and any deviations from the study protocol in the SAP.

DATA COLLECTION AND QUALITY ASSURANCE/DATA MANAGEMENT

DATA HANDLING

Every center will use a specific abbreviation (eg. Salzburg – SBG). Individual patients will be identified using a number (eg. First patient in Salzburg: SBG – 001).

DATA COLLECTION FORMS - ELECTRONIC CRF

Every center will have access to the electronic centralized case report form *ClinCase* (Quadrantek Data Solutions Ltd., Berlin, Germany). *ClinCase* is a validated EDC (electronic data capture) and CDM (clinical data management) system for all types and phases of clinical trials and registries. It complies fully with FDA 21 CFR part 11 and EU GMP Annex 11 regulations. A backup paper version will be available to all centers.

QUALITY ASSURANCE AND MONITORING

Monitoring and audits shall be performed during the clinical trial for the purpose of quality assurance. Details will be specified in the Monitoring Manual.

ETHICAL CONSIDERATIONS AND COUNTRY-SPECIFIC INFORMED CONSENT PROCEDURE

The study will be performed according to national laws, the Declaration of Helsinki and current ICH-GCP guidelines and will be submitted to the Ethics Committees of each participating country.

INFORMED CONSENT PROCEDURE

One important aspect in critically ill patients is informed consent. The majority of patients will not be able to give informed consent at the time of study inclusion due to altered state of consciousness. Only a minority of patients will be able to give full informed consent during the acute setting.

Country specific regulations when immediate informed consent is not possible

Whenever possible, written informed consent will be obtained directly from the patient or from a legal surrogate. The majority of patients, however, will not be able to give informed consent due to acute illness (e.g. sepsis), intubation, mechanical ventilation and sedation. Only a minority of patients will be able to give full informed consent in the acute setting. Based on the VITdAL trial, we assume that >80% of patients will not be able to give informed consent at the time of randomization.

The following procedures will be applied:

- Patient with full consent or available legal surrogate → Immediate informed consent
- Patient not able to consent → country specific regulations as detailed below
- Patient recovers to full consent → retrospective informed consent

Patient information and informed consent will be handled according to the rules of “Good Clinical Practice” and the “Declaration of Helsinki”. All eligible patients will undergo the consent process prior to randomization as described above using different forms.

Country specific regulations apply in case patient is not able to consent:

Austria:

Deferred/surrogate informed consent (IC)

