FIGURE 1: Schematic Study Design

TRIAL POPULATION

The trial population consists of mixed adult critically ill patients anticipated to require > 48 hours of ICU care at the time of screening with documented vitamin D deficiency using local routine testing (25(OH)D \leq 12 ng/ml (= 30 nmol/L) or undetectable) recruited in several countries in academic and non-academic hospitals.

INCLUSION AND EXCLUSION CRITERIA

INCLUSION CRITERIA

- Patients \geq 18 years
- Anticipated ICU stay \geq 48 hours
- Admission to ICU \leq 72 hours before screening
- Severe vitamin D deficiency (\leq 12 ng/ml or undetectable) using local routine testing after ICU admission

EXCLUSION CRITERIA

- Severe gastrointestinal dysfunction/ unable to receive study medication
- DNR order/imminent death
- Hypercalcemia (> 2.65 mmol/l total calcium and/or > 1.35 mmol/l ionized calcium at screening)
- Known kidney stones, active tuberculosis or sarcoidosis (within the last 12 months)
- pregnancy/lactation (routine pregnancy test at ICU admission)
- other reasons (e.g. geographical reasons, diagnosed advanced dementia)
- hypersensitivity to drug or excipient

STUDY ENROLLMENT PROCEDURES/SUBJECT WITHDRAWAL CRITERIA

Local investigators will identify potential study participants within their ICU during routine care. A screening log documenting the reasons for exclusion from the trial will be kept within the electronic data management system ClinCase.

Informed consent will be sought before study inclusion whenever possible. In case when this is not feasible at the time of study inclusion, surrogate or deferred informed consent will be acceptable. Country specific regulations apply as detailed in the ethical consideration section. Withdrawal of a patient may be decided by the investigators, ie. in the case of severe hypercalcemia. In such cases, treatment may also be unblinded if the local investigator wishes to do so.

INTERVENTIONS

The intervention is a pharmacological dose of cholecalciferol (vitamin D3) versus placebo in an otherwise identical oily solution of medium chain triglycerides (MCT), either given by nasogastric or jejunal feeding tube or swallowed. We use the preparation that is commercially available in Austria (Oleovit, 12.5ml per bottle, 400 IU per drop, total dose of 180,000 IU per bottle).

In detail, the used intervention will be:

- Vitamin D: oral/enteral pharmacological dose of cholecalciferol (vitamin D3)
 - **total dose 900,000 IU**

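### The primary set labelled intention-to-treat is a modified one: it omits undosed patients and patients who live to refuse deferred consent. Bias between arms is probably small, but the definition should be corrected

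*Protocol*

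**What the plan says.** All references are to the protocol.

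- **Dosing.** Under the heading Intention-to-treat population: "The ITT will include all patients who receive at least the loading dose of the study medication". Those included keep their randomised arm: "All patients included here will be analysed according to the treatment assignment during randomisation". The per-protocol and safety sets also require a dose, so no defined set holds all randomised patients.
- **Time origin.** The sections on the primary outcome, Visit 1 and the analysis of the primary outcome all count the 28 days from the loading dose.
- **Refused consent.** The section that defines the analysis sets opens with this rule: "Study participants who do not provide an informed consent after regaining consciousness and refuse to provide any more information are excluded from the study". Both conditions must be met: no consent, and refusal of further information. Its reach is complete, since such patients "will not be included in any statistical analysis".
- **How common deferred consent is.** Under the informed consent procedure: "we assume that >80% of patients will not be able to give informed consent at the time of randomization".
- **Withdrawal.** Under the enrolment and withdrawal section: "Withdrawal of a patient may be decided by the investigators, ie. in the case of severe hypercalcemia". Local unblinding is permitted in that case. The missing-data section rules out imputation, and the interim analysis counts patients who left the study early as having reached their assessment.

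**The concern.** Intention-to-treat protects the randomised comparison because nothing that happens after randomisation decides who is counted. Two rules here break that. The dosing rule removes patients on an event after randomisation and leaves them with no time origin for the primary outcome. The consent rule is more delicate because the endpoint is death. Patients who die without regaining consciousness stay in as deaths, while some who recover can take themselves out. With most patients expected to enter without their own consent, this route is open to a large part of the trial. If refusal differed between arms, a mortality difference could appear where none exists.

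Withdrawal raises a related but separate question. If follow-up ends when an investigator withdraws a patient for hypercalcaemia, which the protocol lists as potentially drug-related, the survival time is censored for a reason that may be linked to treatment.

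**Working it through.** **1. The plan's own sample size.** Inputs from the sample size section: mortality 25% v 20%, two-sided alpha 0.05, power 80%. HR = ln 0.80 / ln 0.75 = 0.776. Freedman events = (1.960 + 0.842)² × [(1 + 0.776)/(1 − 0.776)]² = 491.7 with the unrounded HR. Dividing by the mean mortality 0.225 gives 2,185.4, or 1093 per group, as stated. O'Brien-Fleming spending at half the information inflates this by 1.0037, to N = 2194 and 494 events, as stated. The design figures are sound and serve as the base below.

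**2. Equal refusal.** With true 28-day mortality d, and a fraction r of day-28 survivors removed, observed mortality = d / [d + (1 − d)(1 − r)]. The values of r are assumptions.

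| r in both arms | Placebo | Vitamin D | Difference | Odds ratio | HR |
|---|---|---|---|---|---|
| 0 | 25.0% | 20.0% | 5.0 | 0.75 | 0.776 |
| 5% | 0.25/0.9625 = 26.0% | 0.20/0.96 = 20.8% | 5.1 | 0.75 | 0.777 |
| 10% | 0.25/0.925 = 27.0% | 0.20/0.92 = 21.7% | 5.3 | 0.75 | 0.778 |

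Both odds are divided by the same (1 − r), so the odds ratio cannot change. With no true effect the difference stays exactly zero.

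**3. Unequal refusal, no true effect** (25% in both arms, 1200 randomised per arm, normal approximation to a two-proportion test at 5%).

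- 5% v 10% of all survivors: 25.97% v 27.03%, a false difference of 1.05 points. Type I error is about 8.8%.
- The same rates applied only to the 80% with deferred consent (r × 0.8 = 4% v 8%): 25.8% v 26.6%, or 0.8 points. Type I error is about 7.3%.
- 2% v 5% of the deferred-consent survivors (1.6% v 4%): 25.3% v 25.8%, or 0.5 points. Type I error is about 5.8%.

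**4. Cost of counting undosed patients.** The undosed share is not given, so 1%, 3% and 5% are assumed. N = 2400 randomised, no other losses, dosed patients die at 25%/20%, and undosed patients have the same mortality in both arms (varied from 25% to 90%). Power uses the stated boundaries.

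| Undosed | Dosed set only | All randomised |
|---|---|---|
| 0 | 83.4% | 83.4% |
| 1% | 83.0% | 82–83% |
| 3% | 82.3% | 79–81% |
| 5% | 81.5% | 76–79% |

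**5. Withdrawal.** Reading the two sections together, a patient who had the loading dose and is later withdrawn still meets the definition of the primary set and keeps the randomised arm. No section takes that patient out. What is missing is a statement that vital status is still collected.

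**The case against.** The case for leaving the text alone has real weight. The schedule of evaluations puts randomisation and loading dose in the same Day 0 visit, so undosed patients should be few and the clock shift short. Dosing and consent decisions are blinded, the placebo is an otherwise identical oil, and routine vitamin D testing stops after inclusion, so there is little reason to expect either loss to differ by arm. Removing a refuser's data may be required by law. Counts and sensitivity analyses normally belong in the SAP, which is not at hand and which the protocol says prevails. All of this stands, and it lowers the severity. It does not make the label correct, and it does not supply a set of all randomised patients.

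Three stronger readings are tempting and do not hold:

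- A reader might infer that investigator withdrawal is a third exit from the primary set. No section says so, and the definition keeps such a patient in. Nor does any section say that the day-28 sources (the Austrian statistics office, hospital records, telephone) stop at withdrawal. The gap is silence on follow-up, hence possible informative censoring.
- A reader might take the move from 5.0 to 5.3 points under equal refusal as bias. It reflects higher mortality in both arms; the comparison hardly changes.
- A reader might say that deaths always stay in. A patient who wakes, refuses and dies before day 28 is removed as well. The selection is on being alive at refusal, not on day-28 survival itself.

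**Conclusion.** The point holds as a fault of definition with a modest expected effect. The primary set is a modified intention-to-treat set, fixed after randomisation and partly dependent on survival. Equal refusal barely touches the comparison (HR 0.776 to 0.778 at 10%). A material error needs refusal to differ by arm: in the assumed cases the false difference is 0.5 to 1.05 points, against a planned effect of 5. The protocol gives no refusal rate, no undosed share and no reason to expect imbalance under blinding, so those cases show sensitivity and are not forecasts. Local unblinding, or a treatment effect on who recovers enough to refuse, could produce an imbalance, but the documents do not show that either would. Should-fix: a broken randomised comparison is not demonstrated, but the stated rule can be improved cheaply for an endpoint that is easy to ascertain.

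**What to change.** - Define the primary set as all randomised patients, by assigned arm, with time counted from randomisation. Keep the dosed set, named modified intention-to-treat, as a sensitivity analysis.
- For patients who refuse deferred consent, keep data up to the refusal where national law allows and censor there. That censoring may itself be informative, because these patients have recovered consciousness. Where the law requires removal, report the number by arm and add a sensitivity analysis that counts them as alive. For refusals before day 28 this is an assumption, since all that is known is that they were alive when they refused.
- State that vital status at day 28, day 90 and 1 year is still collected after withdrawal from the study or stopping of study medication, where consent and law allow.

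The cost is wording in the protocol, matching wording in the SAP, and a check of consent law in each country. Undosed patients dilute the effect: about 1 point of power or less if 1% are undosed, and roughly 1 to 3 points if 3% are, under the assumptions above.
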